9.4. PET/CT

The patients will then undergo FDG PET/CT scanning within two weeks following consent and baseline visit(s). Should the PET/CT scan not be conducted within two weeks the LCTU should be informed. If the

research site deems the resulting delay in patient management to be unacceptable the patient should be withdrawn from the study and the LCTU informed of this decision.

The PET/CT scan result will first be documented independently of other clinical information. The patient will then be discussed again by the investigator or at the MDT with the results of the PET/CT available. The management decision will be documented at this point D2 (see section 10.2).

9.5. Planned assessments during follow-up phase

Planned study visits will take place every 3 months or when clinically indicated post baseline for 12 months. Each patient will undergo planned management according to standard practice; which may involve pancreatic resection, biopsy, clinical +/-radiological +/-CA19.9 follow up, best supportive care or other therapy such as chemotherapy. All procedures, treatment and outcomes will be recorded on each follow-up CRF form. Follow up assessments have been scheduled for every 3 months to mirror local standard practice throughout the patient journey as closely as possible. Due to the regional distribution of pancreatic referral centres and geographical difficulties the schedule of follow up visits may not be able to be adhered to in every case. If in person visits to research sites are not possible for patients, information collection at follow up time points should be completed over the phone to ensure quality of life and health economics data is collected. All patients must attend their final 12 month follow up visit if still on study at the participating research site.

9.6. EQ-5D and CSRI Questionnaire

The patient will be asked to complete a short validated quality of life questionnaire (EQ-5D) (Appendix D) and a health Economic Form (CSRI – Appendix E) at each study visit. These completed forms should be submitted to the LCTU with the corresponding CRF form. Should patients be unable to attend follow up visits in person the EQ-5D and CSRI questionnaires should be completed over the telephone. A standard script for telephone administration of the EQ-5d questionnaire (Appendix I) will be followed by the researcher.

9.7. WHO Performance status

Performance status must be assessed at each follow-up visit according to the WHO Performance Status (Appendix F) and recorded on the CRF.

9.8. Laboratory Assessments

There are no mandatory laboratory assessments required as part of the study. Local standard practice should be followed throughout the patient journey. However any laboratory investigations conducted should be recorded in the follow-up CRF.

9.9. Concomitant Medication

Data on Concomitant Medication will be collected at the baseline and at each 3 monthly follow-up visit and will contribute to the Health Economics analysis. There are no restrictions on what medication can be used. All chemotherapy should be recorded as standard.

10. Decision Points

10.1. D1

The diagnosis, stage and management plan from the MDT meeting will be recorded in the CRF as D1 at this point. D1 is the decision made by the clinicians UNBLINDED using the usual diagnosis strategy based on the multidetector CT and MDT meeting outcome and following local practices. The decisions will be categorised according to diagnosis, staging and management.

10.1.1. Diagnosis

Diagnosis will be categorised by the following options:

1. Pancreatic ductal adenocarcinoma
2. Peri-ampullary cancer
3. Cholangiocarcinoma
4. Benign cystic neoplasm
5. Malignant cystic neoplasm
6. Pancreatic pseudocyst
7. Chronic pancreatitis
8. Autoimmune pancreatitis
9. Acute pancreatitis
10. Neuroendocrine tumour
11. Lymphoma
12. Metastasis from non pancreatic primary neoplasm
13. Recurrent pancreatic cancer post resection
14. Normal pancreas
15. Other

10.1.2. Staging

Staging will be categorised according to the following options:

1. Resectable (UICC TNM 7th Edition, 2009, classification stage 0, IA, IB, IIA, IIB) [46]
2. Borderline resectable, i.e. defined as up to 2cm of portal/superior mesenteric vein involvement for 180° circumference.
3. Unresectable (UICC TNM 7th Edition, 2009, stage III and IV)
4. Other

10.1.3. Management

Management will be categorised according to one or more of the following options:

1. Resection (+/-prior laparoscopy)
2. Biopsy (EUS/percutaneous)
3. Drainage procedure, e.g. stent or surgical bypass
4. Chemotherapy/trial
5. Best supportive care
6. Clinical follow up +/- further investigation
7. No further management required
8. Other

10.2. D2

After the additional PET/CT scan has been performed the diagnosis, stage and management plan will be re-evaluated by the investigator or at another MDT meeting and will be recorded in the CRF as D2 at that point. Categories will remain the same as D1.

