9.1. Schedule of assessments

Procedures	Screening (MDT)* ♦	Baseline (Day 0)*	D1	Additional Pet/CT	D2	D3 – Actual Management	Follow-Up Schedule					D4 – Reference Standard
							12 weeks	24 weeks	36 weeks	48 weeks/ Study Completion	Premature Discontinuation	
Window for time points (All visit time points are from the Day 0 Baseline visit)				2 weeks ± 4 days			± 2 weeks	± 2 weeks	± 2 weeks	± 2 weeks		
Signed Consent Form		X										
Assessment of Eligibility Criteria	X	X										
Review of Medical History & Demography		X										
MDCT (± MRI/EUS/USS/ERCP)	X*♦	X♦										
Review of Concomitant Medications		X					X	X	X	X	X	
Urine pregnancy test (WCBA) ■		X										
Random blood glucose		X										
PET/CT Scan				X								
CA.19.9	X♦	X♦					X♦	X♦	X♦	X♦		
EQ-5D Quality of Life		X					X	X	X	X		
CSRI form		X					X	X	X	X		
WHO Performance Status		X					X	X	X	X		
Physical Exam	Complete	X										
	Symptom-Directed	X					X	X	X	X		
Assessment of Adverse Events				X								
Clinical Laboratory^	Chemistry U &Es LFT CRP Amylase	X♦	X♦				X♦	X♦	X♦	X♦		
	Haematology FBC Clotting Profile	X♦	X♦				X♦	X♦	X♦	X♦		
Record Diagnosis, management plan and staging			X		X	X						
Reference standard												X

* The patient may have results from one or all of the marked procedures

♦ Procedures carried out according to local practice with regard to patients with suspected pancreatic malignancy, these are not study-specific procedures.

■ Only to be conducted in women of child bearing age (WCBA)

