9.2. Screening for study eligibility

Patients will be assessed for their eligibility for entry into the study during the local MDT meeting. Screened patients should have a suspected pancreatic malignancy with one or more of the following exploratory test completed to be considered for the study:

- Multidetector CT scan
- Serum bilirubin test
- Serum CA 19.9 test

The patient management plan and clinical decisions made at this point will be documented on the D1 CRF.

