9.3. Baseline assessments

After patients have consented to study participation and signed the informed consent form, baseline assessments should be performed prior to study registration in order to confirm eligibility. The PET/CT scan should be performed within 2 weeks (\pm 4 days) of the baseline visit. This is to ensure patients are not delayed in their diagnostic and management pathway due to participation in the study. The baseline assessments include the following:

- Informed Consent – taken prior to any other study procedures
- Assessment of eligibility criteria
- Review of medical history & demography
- Review of concomitant medications
- EQ-5D Quality of Life
- WHO performance status
- Physical exam (complete and symptom-directed)
- CSRI questionnaire
- Urine pregnancy test (WCBA)
- Random blood glucose

The patients will undergo the following investigations according to standard clinical practice:

Clinical Laboratory

Chemistry

- U & Es (i.e. urea and electrolytes)
- LFT
- CRP
- Amylase
- CA.19.9

Haematology

- FBC
- Clotting Profile

Further diagnostic investigations including:

- Multidetector Computed Tomography (MDCT)
- Endoscopic Ultrasound (EUS)
- Endoscopic Retrograde Cholangiopancreatography (ERCP)
- Magnetic Resonance Cholangiopancreatography (MRCP)

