10.5.1. Reference Standards

The reference standard for diagnosis will be a clinical judgement made by an independent panel based on histology (either biopsy or resection) or clinical outcome at the 12 month assessment. Estimated patient numbers for biopsy are 150, resection 300 and follow up 150. The panel will agree on the appropriate staging for each patient with pancreatic cancer and appropriate management – to be used as reference diagnoses D4.

10.5.2. Stage 1

The panel will initially receive a patient histology report for the target conditions:

- Pancreatic cancer (for the primary objective)
- Stage of pancreatic cancer (UICC TNM 7th Edition, 2009, classification as above for resectable, borderline resectable and unresectable disease)
- Chronic pancreatitis
- Particular types of pancreatic tumour.

In addition to this they will be provided with information about the clinical status of the patient at 12 months (but excluding all information from investigations made at baseline and the PET/CT test results). This will be according to the minimum dataset of the Royal College of pathologists [47], in a standard format for resection histology, this will include pathological staging (pTNM) for tumours.

10.5.3. Stage 2

If the panel is unable to make a firm reference diagnosis based on the above information, results of baseline investigations will be released but not the PET/CT investigation.

The two stage process is planned so that the panel's initial decision is not contaminated by the standard work up of either set of test results, and never by the PET/CT scans results and avoids incorporation bias. Finally the panel will also be asked to judge the appropriateness of management for each patient and if a change prompted by PET/CT was appropriate.

11. NCRI PET Core lab

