11.5. PET/CT Central Reporting

A central PET/CT reporting facility has been established at the Paul Strickland Scanner Centre at Mount Vernon Hospital, in addition to the designated Core Lab, to provide central PET/CT reports independent of the local hospital, reviewed by two experts in clinical PET/CT and to perform second stage quality assurance on all PET/CT scans. Data will be transferred from the Core lab to the Central reporting facility. Central clinical reports will be produced independently by two designated radiologists expert in PET/CT. If there are any significant differences in the local and central reports the local and central laboratory radiologists will confer and agree on a final report and the principal investigator will be informed. To ensure a full report can be produced the central reporting facility must be in receipt of the following;

- PET/CT Report
- Clinical Details
- PET/CT Request
- CT scan from MDT meeting

Contacts at the central reporting facility;

[name] [name] (Clinical Queries)

Paul Strickland Scanner Centre,
Mount Vernon Hospital,
[name].
[contact]
[contact]
[contact]
Email: [contact]

[name] (QA Queries)

Paul Strickland Scanner Centre
Mount Vernon Hospital
[name].
[contact]
[contact]
[contact]
Email: [contact]

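### D2 has no latest time, so EUS, ERCP or biopsy results reported after D1 can enter D2 and bias the D1-versus-D2 comparison towards PET/CT

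*Protocol*

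**What the plan says.** - **D1.** Protocol sections 8.1 and 9.2 set D1 at the screening MDT: "The patient management plan and clinical decisions made at this point will be documented on the D1 CRF".
- **After D1.** Section 9.3 lists EUS and ERCP among the investigations that patients undergo as standard practice. Section 4.2 says that EUS may yield histology and ERCP cytological brushings. Biopsy is itself one of the D1 management options (section 10.1.3).
- **PET/CT.** Section 9.3: "The PET/CT scan should be performed within 2 weeks" of baseline, with a tolerance of 4 days.
- **D2.** Section 9.4: "The management decision will be documented at this point D2", once the PET/CT result is available. Section 10.2: the case "will be re-evaluated by the investigator or at another MDT meeting and will be recorded in the CRF as D2 at that point".
- **Schedule 9.1.** The window row states that "All visit time points are from the Day 0 Baseline visit". It has entries for the scan and the follow-up visits but none for D2.
- **D3.** Section 10.4 records actual diagnosis and management, including pathology and operative details.
- **D4.** Section 10.5.1: an independent panel's judgement "based on histology (either biopsy or resection) or clinical outcome at the 12 month assessment". Of 600 patients, 150 are expected to have biopsy, 300 resection and 150 follow-up only.
- **Analysis.** Section 12.4 compares D1 and D2 sensitivity and specificity against D4 using McNemar's test. It also analyses the PET/CT result itself against D4.

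**The concern.** D2 is meant to differ from D1 only by the PET/CT result. The text says what must come before D2 (the scan) but not what must not. A site that follows the protocol exactly may record D2 after a biopsy, EUS sample or ERCP brushing taken since D1 has been reported.

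That tissue can change D2 but not D1, and it may be the material on which D4 rests, so such a D2 will tend to agree with D4 whatever the scan showed. The protocol takes care to keep PET/CT results away from the D4 panel (section 10.5.3), but does not guard the reverse path, from D4's histology into D2. At stake is whether a gain from D1 to D2 can be credited to PET/CT.

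**Working it through.** **Plan's own figures.** Section 12.2 gives 87 to 281 diseased and 57 to 221 non-diseased patients. The paired relative-accuracy formula is n = ((1.960 + 0.842)/ln g)² × ((g + 1)p₁ − 2p₁₁)/(g p₁²). Here p₁ is the first test's rate, g the ratio of the two rates, and p₁₁ the joint positive rate at its two extremes. For 81% to 90% it gives 87.3 and 281.3. For false-positive rates of 34% to 20% it gives 57.4 and 221.4. 281/0.47 = 598, stated as 600. The planning inputs are therefore read correctly.

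**Inputs for the check.** 500 patients (section 12.3), 47% prevalence, D1 sensitivity 81% and specificity 66% (section 12.2).
- Diseased: 500 × 0.47 = 235. D1 false negatives: 235 × 0.19 = 44.7.
- Non-diseased: 265. D1 false positives: 265 × 0.34 = 90.1.

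**How few corrections are enough.** If the scan adds nothing and all changes go one way, the exact two-sided McNemar p for k changes is 2 × 0.5^k.
- k = 5: p = 0.0625. k = 6: p = 0.031.
- Six is 6/44.7 = 13% of the false negatives, or 6/90.1 = 7% of the false positives.

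**Chance of a false significant gain.** Let f be the share of D1 errors corrected at D2 by tissue already known. The documents give no value for f, so it is an assumption. Random switching between D1 and D2, as a share of patients in each direction, is also assumed. Simulated exact McNemar, counting significant results in favour of PET/CT:

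| f | Sensitivity: 0 / 2% / 5% switching | Specificity: 0 / 2% / 5% switching |
|---|---|---|
| 0 | 0% / 1.0% / 1.6% | 0% / 1.1% / 1.5% |
| 5% | 3% / 5% / 4% | 29% / 14% / 9% |
| 10% | 29% / 15% / 9% | 89% / 46% / 27% |
| 20% | 89% / 48% / 28% | nearly 100% / 92% / 75% |

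The nominal rate in the favourable direction is 2.5%. The apparent gain is 19f points for sensitivity and 34f for specificity: 1.9 and 3.4 points at f = 10%.

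**If only the biopsy group can leak.** That group is 150/600 = 25%. With errors spread evenly (an assumption), it holds 44.7 × 0.25 = 11.2 false negatives and 90.1 × 0.25 = 22.5 false positives. Six corrections then need 6/11.2 = 54% or 6/22.5 = 27% of them.

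**The case against.** **The order is implied.** D2 records a plan whose options include biopsy and resection, and section 10.4 assigns pathology and operative details to D3. A reader might infer that D2 could be written after the operation. The documents do not support this, since it would defy the stated sequence. The order does not, however, exclude tissue from a biopsy, EUS or ERCP done before D2.

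**The scan is also assessed alone.** Section 9.4 has the PET/CT result documented first, independently of other clinical information. Section 12.4 compares it with D4 and builds an incremental regression, and then sets accuracy against impact. A reader might infer that the whole primary objective is compromised. It is not: the weakness lies in the D1-versus-D2 comparison. That comparison is still the plan's initial analysis of incremental benefit.

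**Delay is not shown.** When reports differ significantly, "the local and central laboratory radiologists will confer and agree on a final report" (section 11.5), but nothing says that D2 waits for this, and Appendix G asks for prompt transfer. Waiting for central consensus cannot be counted as a cause. The point does not need it, because D2 has no latest time in any case.

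**D1 may close later than screening.** Schedule 9.1 lists D1 after Baseline. If D1 includes the baseline investigations, the exposure narrows to tissue reported between then and D2. It does not disappear.

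**Tissue is fallible.** Section 4.2 cites 85% to 90% sensitivity and 95% specificity for EUS with FNA, so not every change would be a correction. This lowers the figures above where D4 comes to rest on later evidence.

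**Conclusion.** The gap stands. As written, D2 may contain biopsy or cytology results that D1 could not have and that also feed D4, and the resulting bias favours PET/CT in the diagnostic impact comparison. Few such patients matter: six one-way corrections suffice when nothing else changes. Specificity is the more exposed measure, because about 90 D1 false positives are expected against about 45 false negatives.

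The size rests on assumptions: the leak rate, the amount of other switching, D1 accuracy equal to the planning values for CT, and tissue that agrees with D4. A reader might infer that a useless scan would probably show a significant gain. The documents do not support that, since they do not say how often tissue precedes D2. With leakage confined to the biopsy group, a large share of that group's errors would have to be affected. The point is a bias that the written rule permits, not one shown to occur. Because an analysis plan cannot recover what the D2 recorder knew if the form did not capture it, the rule belongs in the protocol and should be added.

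**What to change.** 1. State in sections 9.4 and 10.2 that D2 is the decision made on the D1 information plus PET/CT. It is dated and signed before the recorder sees any histology or cytology reported after D1.
2. Add to the D2 form the decision date and a tick for whether such tissue was known.
3. Keep all patients in the main analysis. Add a pre-stated sensitivity analysis of D1 versus D2 in two versions: one excludes flagged patients, the other sets their D2 equal to D1. Exclusion alone is not enough, because it selects on early tissue.
4. For patients already entered, apply the same check from existing dates. Section 18 has the forms signed and dated, and D3 collects the pathology report.

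Receipt of D2 at the trials unit before any tissue is reported need not be required; it is impractical with paper forms.

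The cost is the added D2 form entries, a date check at the trials unit, one sensitivity analysis and some flagged D2 forms. Clinical care is unchanged.

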10.3. Certainty

For all the diagnosis, staging and management options listed in D1 and D2 the MDT will record a level of certainty categorised as:

1. Very certain
2. Moderately certain
3. Uncertain

10.4. D3

The actual diagnosis and management of each patient will be recorded on the D3 CRF, as this may differ from the D2 time point. Include any pathology details + report (resection/biopsy), operative details and actual therapy administered.

10.5. D4

10.5.1. Reference Standards

The reference standard for diagnosis will be a clinical judgement made by an independent panel based on histology (either biopsy or resection) or clinical outcome at the 12 month assessment. Estimated patient numbers for biopsy are 150, resection 300 and follow up 150. The panel will agree on the appropriate staging for each patient with pancreatic cancer and appropriate management – to be used as reference diagnoses D4.

10.5.2. Stage 1

The panel will initially receive a patient histology report for the target conditions:

- Pancreatic cancer (for the primary objective)
- Stage of pancreatic cancer (UICC TNM 7th Edition, 2009, classification as above for resectable, borderline resectable and unresectable disease)
- Chronic pancreatitis
- Particular types of pancreatic tumour.

In addition to this they will be provided with information about the clinical status of the patient at 12 months (but excluding all information from investigations made at baseline and the PET/CT test results). This will be according to the minimum dataset of the Royal College of pathologists [47], in a standard format for resection histology, this will include pathological staging (pTNM) for tumours.

10.5.3. Stage 2

If the panel is unable to make a firm reference diagnosis based on the above information, results of baseline investigations will be released but not the PET/CT investigation.

The two stage process is planned so that the panel's initial decision is not contaminated by the standard work up of either set of test results, and never by the PET/CT scans results and avoids incorporation bias. Finally the panel will also be asked to judge the appropriateness of management for each patient and if a change prompted by PET/CT was appropriate.

11. NCRI PET Core lab

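### D2 influences whether D4 rests on histology or on 12-month outcome, so the D1-versus-D2 comparison is open to differential verification of unknown net direction, and the claim that PET/CT never contaminates the panel is too strong

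*Protocol*

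**What the plan says.** Protocol 10.5.1 makes D4 "a clinical judgement made by an independent panel based on histology (either biopsy or resection) or clinical outcome at the 12 month assessment", and expects this split of evidence: "Estimated patient numbers for biopsy are 150, resection 300 and follow up 150".

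The scan reaches the treating team before that evidence is gathered. Under 9.4 the patient is discussed again with the PET/CT available: "The management decision will be documented at this point D2". Section 9.5 continues: "Each patient will undergo planned management according to standard practice; which may involve pancreatic resection, biopsy, clinical +/-radiological +/-CA19.9 follow up". Section 10.4 records actual diagnosis and management as D3, "as this may differ from the D2 time point".

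The panel works in two stages. At Stage 1 (10.5.2) it receives histology and 12-month clinical status, "excluding all information from investigations made at baseline and the PET/CT test results". If no firm diagnosis is possible, Stage 2 (10.5.3) releases the baseline investigations but not the PET/CT. Section 10.5.3 concludes that the panel's decision is contaminated "never by the PET/CT scans results and avoids incorporation bias". The same section then asks the panel whether a management change prompted by PET/CT was appropriate.

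The comparison in 12.4 sets sensitivity and specificity of D1 and D2 against D4, with McNemar's test on the discordant pairs.

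**The concern.** Hiding the scan from the panel deals with incorporation bias. It does not deal with a reference standard whose kind depends on the test. A patient moved to cancer at D2 is more likely to go to biopsy or resection. A patient moved to benign at D2 is more likely to be followed up.

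Follow-up is a weaker check. The schedule in 9.1 lists no imaging at the follow-up visits, CA19.9 there is marked as local practice, and 9.8 makes no laboratory test mandatory. A cancer cleared at D2 that stays silent for 12 months can become D4 benign. It then leaves the cell that counts against D2 for sensitivity and enters the cell that credits D2 for specificity. Both shifts fall on the discordant pairs that McNemar's test uses.

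The blinding is also narrower than claimed. Only investigation results are listed as withheld. The site's working diagnosis and the treatment given are not on that list, although 9.5 collects them: "All procedures, treatment and outcomes will be recorded on each follow-up CRF form". The closing question on PET/CT-prompted change cannot be answered without knowing of that change, and nothing says the D4 diagnosis has been fixed by then.

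**Working it through.** **The plan's own figures.** With the paired-design formula n = ((z₀.₉₇₅ + z₀.₈₀)/ln g)² × ((g+1)p − 2pp)/(g p²), where p is the first test's rate and pp the joint rate:
- Sensitivity: p = 0.81, g = 0.90/0.81, pp from 0.71 (minimum overlap) to 0.81 (maximum overlap). The formula gives 281.3 down to 87.3 diseased; the protocol states 87 to 281.
- False-positive fraction: p = 0.34, g = 0.20/0.34, pp from 0 to 0.20. The formula gives 221.4 down to 57.4 non-diseased; the protocol states 57 to 221.
- 281/0.47 = 597.9, the stated 600. At the final 500, 0.47 × 500 = 235 cancers and 265 others.

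**How far D2-negative patients lack tissue.** On the 10.5.1 figures, 450 of 600 have histology and 150 of 600 (25%) do not. With 282 cancers and 318 others, and D2 at 81%/66%, D2-positives number 0.81 × 282 + 0.34 × 318 ≈ 336. Even if all of these had tissue, 450 − 336 = 114 of the 264 D2-negatives (43%) would too. At most about 57% of D2-negatives are then verified by follow-up alone.

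**Illustration with no true gain.** D1 and D2 both have sensitivity 81% and specificity 66%, with independent errors and N = 500. Two shares are assumptions, absent from the documents:
- m: D2-negative cancers that D4 labels benign.
- q: benign D1+/D2− patients whom Stage 2 labels cancer.

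Expected cells:
- D1+/D2− cancers: 235 × 0.81 × 0.19 = 36.2
- All D2-negative cancers: 235 × 0.19 = 44.65
- D1+/D2− benign: 265 × 0.34 × 0.66 = 59.5

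Apparent D2 − D1 differences:
- Sensitivity: (36.2m − 59.5q)/(235 − 44.65m + 59.5q)
- Specificity: (36.2m − 59.5q)/(265 + 44.65m − 59.5q)

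The last column gives rejections favouring PET/CT on sensitivity (4,000 simulations, exact McNemar).

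| m | q | sensitivity (points) | specificity (points) | favouring PET/CT |
|---|---|---|---|---|
| 0 | 0 | 0 | 0 | 1.9% |
| 10% | 0 | +1.6 | +1.3 | 4.8% |
| 20% | 0 | +3.2 | +2.6 | 11.6% |
| 30% | 0 | +4.9 | +3.9 | 24.0% |
| 30% | 10% | +2.2 | +1.8 | 7.3% |
| 30% | 20% | −0.4 | −0.4 | 1.6% |
| 10% | 20% | −3.4 | −3.2 | 0.2% |

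In the last row 13.1% of runs reject in total, nearly all in favour of D1. The lean vanishes at q = (36.2/59.5)m ≈ 0.61m.

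**Dependence on discordance.** If only 15% of cancers were discordant (also an assumption), each cell would hold 0.15 × 235/2 = 17.6. Relabelling 10% of D2's misses there gives 1.76/233.2 = +0.8 sensitivity points, about half the figure above.

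**Is a large m credible?** If missed cancers are verified like other D2-negatives, m = 10% needs 0.10/0.57 ≈ 18% of those on follow-up to stay silent for a year, and m = 30% needs 0.30/0.57 ≈ 53%. False-negative biopsies relax this somewhat.

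**The case against.** **D2 does not decide the route.** A reader might infer that the PET/CT-informed plan determines who gets tissue. Section 9.4 only documents that plan, 9.5 refers to standard practice, and D3 exists because actual management may differ. This stands: D2 is an influence. The expected 450 of 600 histologies also mean that many D2-negative patients would have tissue.

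**The direction is not fixed.** A reader might infer that the comparison leans towards PET/CT. The documents do not support that. Patients without a firm diagnosis go to Stage 2, where the panel sees the D1 evidence and never the PET/CT. Section 4.1 gives a median survival of 3-6 months in advanced disease, so many missed cancers would surface within a year. Section 4.2 gives EUS-FNA a sensitivity of 85%-90%, so false-negative biopsies in D2-positive patients would count against PET/CT. This stands as well, but it is not a safeguard. Stage 2 opens only when no firm diagnosis can be made, and a patient who is well at 12 months may be firmly labelled benign at Stage 1. Two opposing biases of unknown size do not correct each other.

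**The leak to the panel is inferred.** No section says that the working diagnosis or treatment is shown before D4. Correct; but none says they are withheld, and the word placing the PET/CT-change question last does not lock the diagnosis.

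**Tables by route belong to the SAP,** which is not shown. Their absence is therefore not the finding. The finding is the route dependence built into the design and the overstatement in 10.5.3; the tables are part of the remedy.

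**Conclusion.** The point holds in limited form. The reference route depends in part on D2, blinding the panel does not remove that, and the claim in 10.5.3 is stronger than its procedure supports. Cancers called benign at D2 and only followed up are the least well checked. Small or slow-growing lesions are the likeliest to stay silent; 4.5 counts cystic lesions and tumours under 2 cm among the hardest to diagnose, and 10.1.1 lists malignant cystic and neuroendocrine tumours.

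The size is unknown. The table rests on assumed m, q, equal accuracy and independent errors. It shows that shares of 10% to 30% could matter beside a planned 9-point sensitivity gain, and that a modest Stage 2 error can cancel or reverse the effect. It is not evidence that the trial will favour PET/CT.

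A reader might also infer that dropping discordant pairs without histology would test robustness. It would not, because it deletes genuine D2 misses that follow-up exposed. With no true gain, no mislabelling and 17.6 pairs each way, dropping half of D2's misses leaves 17.6 against 8.8, a spurious gain of 8.8/226.2 = 3.9 points.

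This should be changed, though it does not invalidate the design.

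**What to change.** 1. **10.5.2 and 10.5.3.** Have the panel fix and record the D4 diagnosis before it sees any D2 or D3 entry, site working diagnosis or PET/CT-derived wording (including in histology reports), and before it answers the question on PET/CT-prompted change. Supply the 12-month status as facts: vital status, cause of death, later histology, and post-baseline findings only, so that Stage 1 does not release baseline tests.
2. **12.4.** Report the D1 by D2 tables by verification route: resection, biopsy, follow-up settled at Stage 1, and Stage 2. Repeat the McNemar comparison as a bounding analysis in which a stated range of shares of discordant patients without histology is reassigned against D2 and, separately, against D1. Do not drop these pairs, and do not make dropping them the robustness criterion.
3. **10.5.3.** State that the panel is blinded to PET/CT results but that the reference route may depend on D2.

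The cost is some redaction by the trials unit, a few more tables, and a headline gain that may look less certain. No extra patients or study procedures are needed.
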